**2.4.4.4.3 Changes in 7-point SMPG from Baseline to Weeks 30 and 56**

The 7-point SMPG profile should be measured at the following 7 points: pre-breakfast and 2 hours post-breakfast, pre-lunch, 2-hour post-lunch, pre-dinner, 2-hour post-dinner, and at bedtime. Two hours postprandial (breakfast, lunch and dinner) is defined as 2 hours after the start of the meal. On days when 7-point profiles are done, fasting pre-breakfast SMPG will be considered as the first point of measurement, ie, "pre-breakfast" time point.

Normally, investigator can only record one entry in the eCRF. In case of multiple records per visit for some participants, the most complete one should be selected; in case of a tie, the one closest to the visit will be selected for analysis. Descriptive statistics and graphs will be presented by treatment group at each visit for each time point.

**2.4.4.4.4 Changes in mean 24-hour SMPG from Baseline to weeks 30 and 56**

The mean 24-hour SMPG (7-point profile) will be calculated as the mean of the plasma glucose values over the 7 time points. The daily average data will be calculated only if at least 4 plasma glucose values are available. Only available plasma glucose values will be used for the

calculation. For example, if the available data are pre-breakfast, post-breakfast, pre-lunch, and pre-dinner, then the daily average will be calculated as (pre-breakfast + post-breakfast + pre-lunch + pre-dinner)/4.

Descriptive statistics and graphical presentations will be presented by treatment group over time.

#### *2.4.4.4.5 Changes in prandial glucose excursion from Baseline to Weeks 30 and 56*

The prandial glucose excursion, defined as the change in plasma glucose value after each meal (breakfast, lunch, or dinner), will be calculated by subtracting the preprandial value from the postprandial value.

Prandial glucose excursion will be summarized by treatment group and over time. Additionally, graphical presentations will be provided as appropriate.

#### *2.4.4.4.6 Rescue therapy used during the treatment period until Weeks 30 and 56 (yes/no)*

Proportions of participants who used rescue therapy during the treatment period until Week 30 and until Week 56 respectively will be summarized.

#### *2.4.4.4.7 Time to initiation of rescue therapy (weeks)*

Time to initiation of rescue therapy is defined as the time from the date of randomization to the date of first rescue therapy in weeks. Participants who did not take any rescue therapy during the study will be censored at the date of study completion/discontinuation. The curve of the cumulative incidence of participants with rescue initiation will be estimated using Kaplan-Meier method by study treatment group.

#### *2.4.4.4.8 Patient reported outcome:*

The Patient Qualitative Assessment of Treatment version 2 (PQATv2) is intended for the collection of participant-perceived benefit-risk of glucose-lowering treatment with IMP. The participants will be asked to complete it from home just before the on-site visits planned at Weeks 30 and 56. If a participant discontinues treatment with IMP during the treatment period, the participant will be asked to complete the PQATv2 at the time of discontinuation.

The analysis of participant-reported outcome (PRO) endpoints will be descriptive with no formal testing. For categorical data, frequency and percentage will be provided by treatment group and overall at scheduled visits. Participants' answers to the open-ended questions of PQATv2 (items #1, 3 and 5) will be analyzed qualitatively and quantitatively, as relevant, using appropriate data analysis software. The analysis method for open-ended questions will be provided separately and the analyses results will not be included in CSR.

#### 2.4.4.4.9 Other exploratory analysis:

- *Analysis to investigate whether the HbA1c decrease depends on the decrease in weight* will be assessed by scatter plots of HbA1c reduction versus weight loss. A cumulative distribution plot will be provided for each of changes in HbA1c and in body weight from Baseline to Week 30 and 56.
- Proportion of participants with HbA1c < 7.0% at Week 30 and 56 with no severe or documented symptomatic hypoglycemia will be assessed by number of participants and percentage by treatment group.
- Analysis of change in weight as a function of baseline BMI will be assessed by descriptive summary statistics at scheduled visits, by baseline BMI categorization (<19, [≥19 to <25], [≥25 to <30], [≥30 to <40], ≥40 kg/m^2) and by treatment group.
- Analysis of proportions of participants with 5% and 10% weight loss at Weeks 30 and 56 will be assessed by number of participants and percentage by treatment group.
- Descriptive statistics of change in waist circumference from baseline to Week 30 and 56 will be provided by treatment group.
- Descriptive statistics of change in the ratio C-peptide (nmol/L)/ FPG (mmol/L) from baseline will be provided by scheduled visit and treatment group.

#### 2.4.5 Analyses of safety data

The summary of safety results will be presented by treatment group on the on-treatment period as defined in [Section 2.1.4](#).

##### *General common rules*

All safety analyses will be performed on the safety population as defined in [Section 2.3.2](#), unless otherwise specified, using the common rules noted below. Safety data in participants who do not belong to the safety population (eg, treated but not randomized) will be listed separately.

- The Baseline value is defined in [Section 2.1.1](#). For WBC and differential counts, the baseline is defined as the last available value before the first injection of IMP where no differential component is missing.
- Last on-treatment value is defined as the value collected at or just prior to the last IMP intake.

- The potentially clinically significant abnormality (PCSA) values are defined as abnormal values considered medically important by the Sponsor according to predefined criteria/thresholds based on literature review and defined by the Sponsor for clinical laboratory tests, vital signs, and ECG (PCSA version 3 date dated 21 May 2014 effective date 24 May 2014 [[Appendix B](#)]).
- PCSA criteria will determine which participants had at least 1 PCSA during the 56-week on-treatment period, taking into account all evaluations performed during the 56-week on-treatment period, including nonscheduled or repeated evaluations. The number of all such participants will be the numerator for the 56-week on-treatment period PCSA percentage.
- The treatment-emergent PCSA denominator by group for a given parameter will be based on the number of participants assessed for that given parameter in the 56-week on-treatment period by treatment group on the safety population.
- For quantitative safety parameters based on central laboratory/reading measurements, descriptive statistics will be used to summarize results and change from Baseline values by visit and treatment group.
- The analysis of the safety variables will be essentially descriptive and no systematic testing is planned. Relative risks between treatment groups and their 95% CIs may be provided, if relevant.
- Selected safety analyses will be summarized by age group, gender, racial subgroups, and any pertinent subgroups as appropriate.

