### 1.3 SCHEDULE OF ACTIVITIES (SOA)

Procedure	Screening (up to 3 weeks)		Treatment Period (56 Weeks)												Post treatment Follow-up (6 wks)	Notes
	1	2	3	4	5	6	7	8	9	10	11	12	13	14		
Visit			R					☎			☎		☎	EOT	EOS	
Week	-3	-1	0 base- line	2	4	8	12	18	24	30	36	43	50	56 a	Last IMP+6 weeks	
Acceptable range (days)	-21 to -11	-7 (±3)	1	14 (±3)	28 (±3)	56 (±3)	84 (±3)	126 (±3)	168 (±3)	210 (±3)	252 (±5)	301 (±5)	350 (±5)	392 (±5)	434 (±7)	V2 can be done as soon as the screening eligibility is confirmed V3 can be done 4 to 10 days after V2 V3 should be done at least 11 days after V1 (to allow IMP to be sent to the site) and no later than 21 days after V1
Injection of weekly dose on the day of visit			X	X	X		X		X	X						Participants will self-administer the injection only after blood samples (if any) have been drawn at the respective visit.
Injection of weekly dose may be on a different day than visit						X		X			X	X	X	X		See Table 2 for details of dosing windows
Informed consent	X															Informed consent taken prior to any study-related procedures being performed.
Inclusion and exclusion criteria	X	X	X													Check eligibility before V2 and before randomization
Demography, medical/surgical history	X															Includes diabetes complications, CV and allergy history, alcohol and smoking habits.
Physical examination	X		X				X		X		X		X			

Procedure	Screening (up to 3 weeks)		Treatment Period (56 Weeks)												Post treatment Follow-up (6 wks)	Notes
	1	2	3	4	5	6	7	8	9	10	11	12	13	14		
Visit			R					☎			☎		☎	EOT	EOS	
Week	-3	-1	0 base- line	2	4	8	12	18	24	30	36	43	50	56 a	Last IMP+6 weeks	
Acceptable range (days)	-21 to -11	-7 (±3)	1	14 (±3)	28 (±3)	56 (±3)	84 (±3)	126 (±3)	168 (±3)	210 (±3)	252 (±5)	301 (±5)	350 (±5)	392 (±5)	434 (±7)	V2 can be done as soon as the screening eligibility is confirmed V3 can be done 4 to 10 days after V2 V3 should be done at least 11 days after V1 (to allow IMP to be sent to the site) and no later than 21 days after V1
Vital signs	X		X		X	X	X		X	X		X		X	X	BP and HR in sitting position after at least 5 minutes of rest.
Height	X															
Body weight	X		X	X	X	X	X		X	X		X		X	X	
Waist circumference			X							X				X		See Section 8.1.4
12-lead ECG			X				X							X		The 12-lead ECG recording should be obtained in supine position prior to IMP dose administration. See Section 8.2.3 .

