a In case of premature permanent IMP discontinuation, participants should have a visit as soon as possible after last IMP administration with the assessments normally planned for EOT visit (including a PK sample if the visit can be scheduled 7 days after the permanent IMP discontinuation). Afterwards, the participants should continue in the study up to the scheduled date of study completion and be followed up according to the study procedures as specified in the protocol. Every effort should be made to have the participant complete the Week 56 Visit assessments (primary and main secondary endpoints) as the minimum. For safety reasons, participants who do not want to continue to be followed in the study after IMP discontinuation, should be assessed 6 weeks (±1 week) from the last IMP dose (at the minimum) using the procedure normally planned for the post-treatment follow-up visit at EOS. At the time corresponding to their Week 56 Visit, all attempts will be made to contact the participants to inquire about safety/vital status.

Abbreviations: ADA: antidrug antibody, AE: adverse event, β-HCG: beta-human chorionic gonadotropin, BP: blood pressure, CV: cardiovascular, ECG: electrocardiogram, EOS: end of study, EOT: end of treatment, FPG: fasting plasma glucose, FSH: follicle-stimulating hormone, HbA1c: hemoglobin A1c, GI: gastrointestinal, HR: heart rate, IMP: investigational medicinal product, IRT: interactive response technology, PK: pharmacokinetics, PQATv2: Patient's Qualitative Assessment of Treatment version 2; PROMIS: Patient-Reported Outcomes Measurement Information System; R: Randomization; SAE: serious adverse event, SMPG: self-monitored plasma glucose, WOCBP: women of childbearing potential

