**Dosing instructions**

The injection interval of the IMP is once weekly, preferably on the same week day (eg, each Monday) at any time of the day. Injections should be administered SC to any of the following body regions: abdomen, thigh, or upper arm. Within any selected region, the site of injection should be changed (rotated) at each time to prevent skin reactions. The region, date, and time of administration should be recorded for each injection administered.

For selected visits during the Treatment Period up to Week 30 (corresponding to predose PK sample collection) the weekly dose will be administered at the study site after blood sample collection (see SoA, [Section 1.3](#)).

For the other weekly administrations, if a dose is missed, participants must be instructed to administer it as soon as possible if there are at least 3 days (72 hours) until the next scheduled dose. If less than 3 days remain before the next scheduled dose, the participant should skip the missed dose and administer the next dose on the regularly scheduled day. In each case, participants can then resume their regular once-weekly dosing schedule. The day of weekly administration can be changed if necessary as long as the last dose was administered 3 or more days before (see [Section 7.1.2.1](#)).

Participants will be asked to administer the last 2 consecutive weekly dose injections prior to PK sampling at the same body region (eg, at Week 2 and Week 3 before the planned PK visit at Week 4; see [Section 8.5](#)).

Predose PK samples are expected to be collected at least 6 to 7 days after last dose of IMP. The corresponding study visits (Visit 5, Visit 7, Visit 9 and Visit 10) and the timing of dose administration before each of these visits should be scheduled to ensure, as much as possible, the duration of 6 to 7 days between them is maintained.

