**IMP dose schedule**

	Dose 1	Dose 2	Dose 3	Dose 4	Dose 5
	Day 1	Week 1	Week 2	Week 3	Week 4
	Visit 3		Visit 4		Visit 5
Dosing	(on-site)	(at home)	(on-site)	(at home)	(on-site)
Epeglenatide 4 mg	2 mg	2 mg	4 mg	4 mg	4 mg
Epeglenatide 6 mg	2 mg	2 mg	4 mg	4 mg	6 mg
Dulaglutide 1.5 mg	0.75 mg	0.75 mg	1.5 mg	1.5 mg	1.5 mg

From Week 4 (Visit 5) through the rest of the treatment period, participants will remain on the randomized IMP dose until the EOT at Week 56 (Visit 14).

**Storage conditions** Store between +2°C and +8°C (36°F and 46°F). Do not freeze, protect from light.

**Packaging and labeling** Study treatment will be provided in boxes, in accordance with the administration schedule. The content of the labeling is in accordance with the local regulatory specifications and requirements.

The details of this table are specific to IMP; information of non-IMP is described separately in this [Section 6.1.2](#).

EOT: end of treatment, IMP: investigational medicinal product, PK: pharmacokinetics, SC: subcutaneous, SoA: schedule of activities

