##### *Observation period*

The period related to treatment will be divided into 3 main segments:

- The **pre-treatment** period is defined as the time from informed consent up to the time of first injection of open-label IMP
- The **on-treatment** period is defined as the time from the first injection of the open-label IMP up to 30 days (7 days for hypoglycemia) after the last injection of the IMP
- The **post-treatment** period is defined as the period from the end of the on-treatment period.

The **on-study observation period** is defined as the time from first injection of open-label IMP up to either the last protocol-planned visit or the date of last available information if participants discontinue the study prematurely, whichever is later.

The **post-study observation period** is defined as the time after the end of the on-study observation period until the date of resolution/stabilization of SAE, AESI, and AERSM, up to database lock.

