#### **Summary statistics at scheduled visits**

Summary statistics (for Screening value, Baseline value, observed values, and observed changes from Baseline) at scheduled visits will be provided by treatment group for HbA1c value over the treatment period. The last on-treatment value will be presented in a separate row. The summary will include the number of observations, mean, SD, SE, minimum, median, and maximum. Graphical presentations will also be used to examine trends over time using mean values (±SE) and mean changes from Baseline (±SE) at each of the scheduled visits (using OC).

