#### **2.4.5.4 Analyses of laboratory variables**

All hematology and clinical chemistry results will be listed by treatment group, participants and visit, including scheduled and unscheduled/repeat measurements.

The summary statistics (including number, mean, median, standard deviation, minimum and maximum) of all protocol-required laboratory variables (central laboratory values and changes from Baseline) will be calculated for each scheduled visit and last value on treatment by treatment group. This section will be organized by biological function as specified in [Section 2.1.4.3](#).

The incidence of PCSAs at any time during the on-treatment period will be summarized by biological function and treatment group whatever the Baseline level and/or according to the following Baseline status categories:

- Normal/missing
- Abnormal according to PCSA criterion or criteria

For parameters for which no PCSA criteria are defined, similar table(s) using the normal range will be provided. For calcitonin, no PCSA criterion is defined. Similar summaries will be provided using the pre-defined categories:  $\leq$ ULN,  $>$ ULN -  $<$  20 ng/L,  $\geq$ 20 -  $<$ 50 ng/L, and  $\geq$ 50 ng/L (Note that ng/L is the standard international unit and is equivalent to pg/mL).

All measurements collected during the on-treatment period, including values from unscheduled visits, will be considered for the PCSA summaries. These summaries will include participants in the safety population who have at least 1 assessment performed during the on-treatment period. When a PCSA definition involves only a change from baseline value, participants must also have a baseline value to be included in the summaries, and when required by the definition of the abnormality, participants must also have available laboratory normal ranges.

For some parameters, such as liver enzymes, the lower limit of normal (LLN) is not considered clinically relevant, and values below this limit are considered normal. When there are multiple PCSA criteria for a specific parameter (eg, ALT), the participant will be counted once during the on-treatment period for the specific parameter in question under the worst/maximum PCSA category.

Elevated liver parameters will be summarized by treatment group in safety population.

For PCSA, both central and local lab data will be used.

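### The SAP's last on-treatment value stops at the last injection, while its on-treatment period runs 30 days further, so early end-of-treatment laboratory values and some or all Week 56 values drop out of that row

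*SAP*

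**What the plan says.** - **Definition.** Under the general common rules of SAP 2.4.5: "Last on-treatment value is defined as the value collected at or just prior to the last IMP intake". No look-back limit is given for the words about being just prior.
- **On-treatment period.** SAP 2.1.4 counts data as on-treatment from the first injection "up to 30 days (7 days for hypoglycemia) after the last injection of the IMP". The opening of SAP 2.4.5 says safety results are summarized on this period.
- **Where the value is reported.** In SAP 2.4.5.4, laboratory statistics "will be calculated for each scheduled visit and last value on treatment by treatment group". For HbA1c, SAP 2.4.4.1 says: "The last on-treatment value will be presented in a separate row". SAP 2.4.4.2.2 asks for the same for FPG and body weight. Neither efficacy section defines the term or cites SAP 2.4.5.
- **Dosing.** Protocol Table 2: "The injection interval of the IMP is once weekly, preferably on the same week day". The Schedule of Activities ticks Visit 14 (Week 56) in the row "Injection of weekly dose may be on a different day than visit".
- **Early stopping.** Footnote a of the Schedule of Activities: "participants should have a visit as soon as possible after last IMP administration with the assessments normally planned for EOT visit".

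**The concern.** A laboratory sample taken a few days after the final weekly injection is on-treatment under SAP 2.1.4 but cannot be the last on-treatment value under SAP 2.4.5. An early end-of-treatment visit is placed after the last dose, so the assessment meant to record status at stopping is the one the rule normally discards.

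The by-visit laboratory rows may not recover it. The rule in SAP 2.5.4 that maps early termination visits to scheduled visits is headed as applying to efficacy parameters, and SAP 2.5.5 keeps unscheduled laboratory values out of by-visit summaries. The last-value row may then be the only summary of laboratory means that could show these results. The sponsor terminated the study early on 9 September 2020 (SAP 2.3.1.2), so stopping before Week 56 is not a remote case, although the documents give no count.

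For completers, one laboratory table could show the Week 56 result in the Week 56 row and an older result in the last on-treatment row.

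**Working it through.** **Inputs.** From the Schedule of Activities: Week 30 is Day 210 (±3), Week 43 is Day 301 (±5), Week 56 is Day 392 (±5), and end of study is Day 434 (±7), described as last IMP plus 6 weeks. Hematology and chemistry are sampled at Weeks 12, 30, 43 and 56; calcitonin at Weeks 12, 30 and 56; lipids at Weeks 30 and 56. Dosing is every 7 days from Day 1.

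**The plan's own timing.** 392 + 6 × 7 = 434, which matches the stated end-of-study day and places the last dose at about Week 56. The exposure formula in SAP 2.4.3.1 (last dose date minus first dose date plus 7) reaches 56 weeks with a last dose on Day 386: 386 − 1 + 7 = 392 = 56 × 7. No IMP is dispensed at Visit 14. The documents therefore leave open whether dose 56 or dose 57 is the last.

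**Which Week 56 values qualify.** Dose k falls on Day 1 + 7(k − 1). The visit window is Days 387 to 397, which is 11 days.

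| Last dose | Day | Window days on or before the last dose |
|---|---|---|
| Dose 56 | 1 + 7 × 55 = 386 | 0 of 11 (visit is 1 to 11 days after) |
| Dose 57 | 1 + 7 × 56 = 393 | 7 of 11 (Days 387 to 393) |

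**How old the earlier value is for an affected completer,** if the latest earlier scheduled sample is used:

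- Hematology and chemistry, from Week 43: 392 − 301 = 91 days. With windows, 387 − 306 = 81 to 397 − 296 = 101.
- Calcitonin and lipids, from Week 30: 392 − 210 = 182 days. With windows, 387 − 213 = 174 to 397 − 207 = 190.

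**Early discontinuers.** Assumptions: last-dose Days 1 to 378 weighted equally, and an end-of-treatment visit 0 to 7 days later (0 is the lower limit; a same-day visit would itself qualify). Age is the visit day minus the last scheduled sampling day on or before the last dose. The middle columns cover cases that have an earlier post-baseline value.

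| Test | Mean age (days) | Longest (days) | 91 days or more | No scheduled post-baseline value |
|---|---|---|---|---|
| Hematology, chemistry | 51 to 58 | 125 to 132 | 12% to 17% | 83/378 = 22% |
| Calcitonin | 75 to 82 | 168 to 175 | 38% to 43% | 22% |
| Lipids | 84 to 91 | 168 to 175 | 46% to 50% | 209/378 = 55% |

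As a share of all scanned days, an age of 91 days or more occurs in 9% to 13% for hematology and chemistry, 30% to 34% for calcitonin and 21% to 22% for lipids.

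**Check of the SAP 2.1.4 window.** A Week 56 visit is at most 397 − 386 = 11 days after the last dose, so it qualifies under either last-dose day. The follow-up sample at 6 weeks ± 1 week is at least 42 − 7 = 35 days after the last dose, so a 30-day limit does not admit it.

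**The case against.** The strongest reply is that this concerns one supplementary descriptive row. That stands. By-visit laboratory rows still report Week 56. The tables of potentially clinically significant abnormalities use every measurement in the on-treatment period, including unscheduled ones, so early end-of-treatment results within 30 days of the last dose reach them. Vital signs have no such row, and no test depends on it.

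Four stronger readings are tempting but not supported:

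- **That most Week 56 values are lost.** This needs a last dose before the visit. With a Day 393 dose, 7 of 11 window days qualify.
- **That every early end-of-treatment value is lost.** A visit on the dosing day counts as being at the last intake.
- **That the replacement is always 3 to 6 months older.** Those ages fit only a Week 56 value replaced by Week 43 or Week 30. Replacement is itself an inference: with no look-back limit, a value that old might be treated as missing.
- **That the HbA1c, FPG and body weight rows are certainly affected.** The definition sits among the safety rules. For efficacy, SAP 2.5.4 maps early termination values to the scheduled visit and accepts values within 30 days of the Week 56 target (7 for FPG).

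These points limit the reach. They do not remove the contradiction between the two rules or the loss of early end-of-treatment laboratory values from the row.

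**Conclusion.** The inconsistency is real and minor. Followed as written, SAP 2.4.5 removes from the laboratory last-value row the early end-of-treatment results not taken on the dosing day, and the Week 56 results of completers last injected before the visit.

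The share of completers affected cannot be stated beyond the two cases worked out, because the last-dose day is open and actual injection days will vary. The 91-day and 182-day figures assume that the latest earlier scheduled value is used. The early-discontinuer figures rest on equal weighting of stopping days, which is an assumption and not trial data. On that basis the earlier value is usually under 3 months older or there is none, though calcitonin and lipids reach 3 months more often than hematology and chemistry. Any effect on the HbA1c, FPG and body weight rows depends on whether the safety definition governs them.

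**What to change.** Replace the sentence in SAP 2.4.5 so that the last on-treatment value is the last value collected within the on-treatment period of SAP 2.1.4, from the first injection to 30 days after the last. State in SAP 2.4.4.1 and 2.4.4.2.2 whether the same definition governs the HbA1c, FPG and body weight rows.

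A separate 7-day window for HbA1c and body weight should not be added. The documents give no such window for these measures, and after a Day 386 dose it would end on Day 393 and still exclude visits on Days 394 to 397.

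The cost is one revised sentence, a short cross-reference and the matching change to the derivation of the row. No new data are needed.
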